### 6.1.3 Safety Data

#### 6.1.3.1 *Adverse Events and Adverse Drug Reactions*

##### 6.1.3.1.1 Adverse Events

An AE is, “any untoward medical occurrence in a patient or clinical trial subject administered a medicinal (investigational or non-investigational) product and which does not necessarily have a causal relationship with this treatment.” An adverse event can therefore be any unfavorable and unintended sign (including abnormal laboratory finding), symptom, or disease temporally associated with the use of a medicinal (investigational or non-investigational) product, whether or not considered related to the medicinal (investigational or non-investigational) product. All AEs will be coded using the latest available version (Version 18.0) of the Medical Dictionary for Regulatory Activities (MedDRA).

A treatment-emergent adverse event (TEAE) is defined as an AE that begins or that worsens in severity during or after first intake of the study drug has been administered.

A pre-treatment AE is defined as an AE that begins before first intake of the study drug.

Any AEs with incomplete start and end dates/times will be treated as follows:

Missing onset dates (where UK and UKN indicate unknown or missing day and month respectively):

- UK-MMM-YYYY: If the month and year are different from the month and year of the first dose of study drug, assume 01-MMM-YYYY. If the month and year are the same as the first

Chiesi

Final 1.0

CCD-5633AA1-02

18/July/2018

---

TP-EP.BS-WW-001-05

Effective date: 29 Jul 15

Related to: SOP-EP.BS-WW-002

Page 14 of 46

## Statistical Analysis Plan

dose of study drug month and year, and the end date (after any imputation) is on or after the first dose of study drug, then assume the date of the first dose of study drug. If the month and year are the same as the first dose of study drug month, and year and the end date (after any imputation) is prior to the first dose of study drug, then assume the end date for the onset date.

- DD-UK-YYYY/UK-UKN-YYYY: If the year is different from the year of first dose of study drug, assume 01-JAN-YYYY of the collected year. If the year is the same as the first dose of study drug year, and the end date (after any imputation) is on or after the first dose of study drug, then assume the date of the first dose of study drug. If the year is the same as the first dose of study drug, and the end date (after any imputation) is prior to the first dose of study drug, then assume the end date for the onset date.

Missing end dates (where UK and UKN indicate unknown or missing day and month respectively):

- UK-MMM-YYYY: Assume the last day of the month;
- DD-UKN-YYYY/UK-UKN-YYYY: Assume 31-DEC-YYYY.

Missing start/end time (where UK and UKN indicate unknown or missing day and month respectively):

- Adverse events with unknown start and/end times (but where the date is known) will be imputed with a time of 00:00 h (start) / 23:59 h (end) for the tabulations but will be shown as UK:UK in the listings (where UK = unknown). If the date is the date of treatment start will be imputed as time of start of treatment following a worst case approach.
- Adverse events with completely unknown start dates will be considered as treatment-emergent for the tabulations and will be shown as UK in the listings.

AE Duration (days) will be computed as follows:

- When both dates are completely known and AE is resolved:

$$\text{Duration (days)} = \text{AE end date} - \text{AE onset date} + 1$$

- When the AE onset date is fully known but the AE is not resolved at the end of the trial:

$$\text{Duration (days)} = \text{date of completion/discontinuation} - \text{AE onset date} + 1$$

In this case the duration will be presented as “>x days” in the listings rather than “x days”

When the AE onset date is incomplete or unknown or when the AE has resolved but with an incomplete or unknown end date, the AE duration will not be calculated, unless otherwise specified.

Chiesi

Final 1.0

CCD-5633AA1-02

18/July/2018

TP-EP.BS-WW-001-05

Effective date: 29 Jul 15

Related to: SOP-EP.BS-WW-002

Page 15 of 46

## Statistical Analysis Plan

AE Relative Day of Onset will be computed as follows

- Relative day of onset for pre-treatment AE:

Relative Day of Onset = AE onset date – reference date

- Relative day of onset for TEAE:

Relative Day of Onset = AE onset date – reference date + 1

where reference date is treatment date/time.

### **6.1.3.1.2 Adverse Drug Reactions**

An ADR is an, “untoward and unintended response to an investigational medicinal product related to any dose administered.”

For further information please refer to Section 10 of the CSP.

### **6.1.3.1.3 Neonatal Morbidities**

The incidence of major neonatal morbidities will be monitored (for the list of neonatal morbidities and complications of prematurity see section 10.8 of the CSP). These include:

- Air leaks (pneumothorax, pneumomediastinum, pneumopericardium, pneumoperitoneum);
- anemia of prematurity;
- apnea of prematurity;
- necrotizing enterocolitis (NEC);
- patent ductus arteriosus (PDA),
- pneumonia;
- pulmonary interstitial emphysema (PIE);
- pulmonary hemorrhage;
- germinal matrix/intraventricular hemorrhage (GMH/IVH);
- cerebral parenchymal hemorrhage;
- neonatal jaundice;
- periventricular leukomalacia (PVL);
- sepsis and/or meningitis;
- Presence of the following abnormal laboratory values:

Chiesi

Final 1.0

CCD-5633AA1-02

18/July/2018

---

TP-EP.BS-WW-001-05

Effective date: 29 Jul 15

Related to: SOP-EP.BS-WW-002

Page 16 of 46

## Statistical Analysis Plan

- hypoglycemia
- hyperglycemia
- hypocalcaemia
- hypercalcemia
- hyponatremia
- hypernatremia
- hypokalemia
- hyperkalemia.

### **6.1.3.2 Clinical Laboratory Tests**

The following safety laboratory parameters will be measured:

- **Biochemistry:** urea, creatinine and electrolytes (sodium, potassium, calcium, phosphorus), alanine aminotransferase (ALT), aspartate aminotransferase (AST), glucose, C-reactive protein.
- **Hematology:** full blood count (FBC).

### **6.1.3.3 Vital Signs**

The following vital signs measurements will be obtained:

- Systolic blood pressure (SBP) [mmHg];
- Diastolic blood pressure (DBP) [mmHg],
- Heart rate (bpm);
- SpO2 during administration [%].

### **6.1.3.4 Physical Examination**

Not applicable.

### **6.1.3.5 Neonatal Concomitant Medications**

Any concomitant medication required for the normal care of preterm neonates will be permitted during the study. Concomitant medication will be coded using the World Health Organization-Drug

Chiesi

Final 1.0

CCD-5633AA1-02

18/July/2018

---

TP-EP.BS-WW-001-05

Effective date: 29 Jul 15

Related to: SOP-EP.BS-WW-002

Page 17 of 46

## Statistical Analysis Plan

Dictionary (WHO-DD) (Version **SEP2015**) and will be classified by Anatomical Therapeutic Chemical (ATC) categories.

### **6.1.3.6     *Surgical/ Medical Procedures***

Any Surgical/ Medical Procedure required for the normal care of preterm neonates during the study conduct will be documented with:

- Has the Subject undergone any Surgical/Medical procedures? (Y/N), if answered yes with:
  - Name of the Procedure;
  - Start/End Date and Time;
  - Adverse Event Number (assigned);
  - Indication: Complication (with number and specification if other mentioned.)

and coded.

### **6.1.3.7     *Immunogenicity Assessment***

Immunogenicity assessment will be carried out in one blood sample collected prior to study treatment administration and approximately at 5 weeks after administration (with a window from 3 to 6 weeks). The measure of anti-SP-B and anti-SP-C antibodies will be evaluated by a titration versus a positive control serum (GP). Further details are given in section 7.2.1 of the CSP.

## **6.1.4       *Pharmacodynamic/Efficacy Data***

### **6.1.4.1     *Ratio of arterial oxygen saturation ( $SpO_2/FiO_2$ )***

Ratio of arterial oxygen saturation determined by pulse oximetry and fraction of inspired oxygen ( $SpO_2/FiO_2$ ) will be determined in the first 7 days post-treatment (at 30 minutes, at 1, 3, 6, 12, 18, 24 hours, at Days 2, 3, 5 and 7), at Day  $28 \pm 2$  PNA, at discharge home and at 36 weeks PMA.

Chiesi

Final 1.0

CCD-5633AA1-02

18/July/2018

---

TP-EP.BS-WW-001-05

Effective date: 29 Jul 15

Related to: SOP-EP.BS-WW-002

Page 18 of 46

## Statistical Analysis Plan

### ***6.1.4.2 Fraction of inspired oxygen (FiO2)***

FiO2 will be measured in the first 7 days post treatment (at 30 minutes, at 1, 3, 6, 12, 18, 24 hours, at Days 2, 3, 5 and 7), at Day 28±2 PNA, at discharge home and at 36 weeks PMA.

### ***6.1.4.3 Arterial oxygen saturation (SpO2)***

SpO2 will be measured in the first 7 days post treatment (at 30 minutes, at 1, 3, 6, 12, 18, 24 hours, at Days 2, 3, 5 and 7), at Day 28±2 PNA, at discharge home and at 36 weeks PMA.

### ***6.1.4.4 Respiratory Severity Score (RSS)***

Respiratory Severity Score (RSS) [FiO2 corrected by mean airway pressure (MAP)] will be calculated at each timepoint (i.e., at 30 minutes, at 1, 3, 6, 12, 18, 24 hours and on Day 2) as FiO2 x MAP.

### ***6.1.4.5 Oxygen Saturation Index (OSI)***

Oxygen Saturation Index (OSI) will be calculated at each timepoint (i.e., at 30 minutes, at 1, 3, 6, 12, 18, 24 hours and on Day 2) as

$$\text{FiO}_2 \times \text{MAP} \times 100 / \text{SpO}_2.$$

### ***6.1.4.6 Ventilator Settings***

MAP (cmH2O), PIP (cmH2O) and PEEP (cmH2O) will be determined in the first 7 days post-treatment (at 30 minutes, at 1, 3, 6, 12, 18, 24 hours, at Days 2, 3, 5 and 7), at Day 28±2 PNA, at discharge home and at 36 weeks PMA.

### ***6.1.4.7 Biomarkers of inflammation***

CXCL8, Interleukin 1β (IL1β), Interleukin 6 (IL6), Tumor Necrosis Factor-alpha (TNF-α), myeloperoxidase (MPO) will be collected prior to study drug administration, at 24±1 hours and on day 2 (48±1 hours) in a subgroup of babies who require endotracheal intubation for mechanical ventilation, when feasible. Additionally, total proteins concentration and CXCL8/total protein, IL1β/total protein, IL6/total protein, TNF-α/total protein, MPO /total protein will also be provided.

Chiesi

Final 1.0

CCD-5633AA1-02

18/July/2018

---

TP-EP.BS-WW-001-05

Effective date: 29 Jul 15

Related to: SOP-EP.BS-WW-002

Page 19 of 46

## Statistical Analysis Plan

### **6.1.4.8 Mortality and BPD**

#### ***Mortality***

The mortality incidence at 36-week PMA and at Day 28 will be compared by treatment as for Mortality/BPD incidence.

#### ***RDS-Mortality***

The RDS-associated Mortality incidence through 14 days of age will be surveyed in the corresponding treatment group. Patients with reasons for discontinuation='RDS RELATED DEATH" and died within 14 days of age will be considered in the counts.

#### ***Bronchopulmonary Dysplasia (BPD)***

BPD is defined according to the diagnostic criteria recently proposed by the NICHD / NHLBI / ORD Workshop [4].

The patients will be diagnosed with BPD and included in the analysis if the following applies:

Has the baby been treated with oxygen >21% for at least 28 days? ='Yes' and 'Did the patient have a diagnosis of BPD?='Yes'.

In addition, if:

- 1) there is no requirement for supplemental oxygen and ventilatory support (i.e. "Is there a requirement for supplemental oxygen?" = "No" and "Is there a requirement for ventilatory support?"="No", BPD will classified as 'Mild'
- 2) if there is requirement for supplemental oxygen (i.e. 'Is there a requirement for supplemental oxygen?" = "Yes") and oxygen value <30% then BPD will be classified as 'Moderate';
- 3) if there is requirement for supplemental oxygen (i.e. 'Is there a requirement for supplemental oxygen?" = "Yes") with an oxygen value  $\geq 30\%$  and/or positive pressure ("Is there a requirement for ventilatory support?"="Yes") then BPD will be classified as 'Severe'

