7.1.9 Phase 9 (Follow-up) – 36-week PMA (from 36⁺⁰ to 36⁺⁶ weeks)

The following information will be collected:

- SpO₂ along with vital signs (systolic and diastolic blood pressure, heart rate);
- FiO₂;
- any change in non-invasive/invasive mechanical ventilation with the relevant dates and times;
- use of oxygen alone (supplemental oxygen without invasive or non-invasive ventilator support) will be monitored and any new occurrence will be recorded with the relevant dates and times;
- cranial sonography if not already performed at phases 7 or 8;
- new neonatal concomitant medications and adverse events as well as changes in those already reported;
- BPD diagnosis (see definition in Appendix II) ;
- 400 µL blood sample for immunogenicity assessments in serum if not already taken at day 28 PNA or at Discharge home, according to what described in paragraph 7.2;

In case the baby was discharged home or transferred to a continuing care site prior to this phase, the baby should be recalled as soon as possible for an on-site clinic visit at the recruiting site. If not feasible, any effort should be made to collect information about the occurrence of BPD, adverse events as well as any change in concomitant medications. The investigator should therefore contact the physician of the continuing care site or the family pediatrician to collect the relevant information.

In the event that multiple measurements are available, the measurements closest to the required time point are to be collected.

7.1.10 Phase 10 – Clinical assessment at 24 months (± 3 months) corrected age

A further clinical assessment will be performed at 24 months (± 3 months) corrected age by physicians of participating study centers. This clinical assessment will be based on:

- Demographic data
- Vital signs
- Bayley Scales of Infant Development (*see Section 7.2.5*)
- Health status questionnaire (health problems, illnesses, injuries, well-being, diet, respiratory assessment).

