10.11 General Notes

- In case of death, a comprehensive narrative report of the case should be prepared by the Investigator and provided to the [REDACTED] Safety Contact together with the Serious Adverse Event form, retaining a copy on site;
- If an autopsy is performed, copy of autopsy report should be actively sought by the Investigator and provided to the [REDACTED] Safety Contact as soon as available, retaining a copy on site;
- If a baby is transferred to a continuing care site prior to discharge home, the investigator should ensure that the receiving hospital site is aware that the baby is participating to the present study and communication should be maintained in order to record any adverse event. Moreover, the investigator of the recruiting site will have to provide the continuing care site with written instruction about management and reporting of SERIOUS AE. After discharge home from the continuing care site a copy of the discharge summary letter should be requested in order to cross reference any adverse events and to determine if the baby is suffering from BPD.

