APPENDIX IV

LIST OF STUDY DEFINITIONS

- ✓ **Air leaks** will be documented by evidence of pneumothorax, pneumomediastinum, pneumopericardium, pneumoperitoneum on radiograph [\(20\)](#).
- ✓ **Anemia of prematurity** is defined by a haemoglobin or haematocrit value that is more than two standard deviation below the mean for age [\(21\)](#)
- ✓ **Apnoea of prematurity** is defined as pause in breathing > 20 sec, or <20 sec if accompanied by bradycardia and/or cyanosis [\(22\)](#)
- ✓ **Bronchopulmonary dysplasia (BPD)** is defined according to the diagnostic criteria recently proposed by the NICHD / NHLBI / ORD Workshop [\(23\)](#):
 - Time point of assessment and general criterion - 36 weeks postmenstrual age (PMA) or discharge home, whichever comes first; treatment with oxygen > 21% for at least 28 days plus the below reported additional criteria:
 - Additional criteria:

Mild BPD = breathing room air at 36 weeks PMA or at discharge;

Moderate BPD = need for < 30% oxygen at 36 weeks PMA or at discharge;

Severe BPD = need for $\geq 30\%$ oxygen and/or positive pressure at 36 weeks PMA or at discharge.
- ✓ **Hypercalcaemia**: Ca tot > 11 mg/dl
- ✓ **Hyperglycaemia**: > 175 mg/dl (in 2 separate occasions at least 6 hours apart)
- ✓ **Hyperkalaemia**: $K^+ > 6,0 \text{ mmol/l}$
- ✓ **Hypernatraemia**: > 150 mEq/l (operational value > 155 or an increasing trend)
- ✓ **Hypocalcaemia**: Ca tot < 7,0 mg/dl
- ✓ **Hypoglycaemia**: < 40 mg/dl (operational values < 45 in day 1st and 50 further days)
- ✓ **Hypokalaemia**: $K^+ < 3 \text{ mmol/l}$
- ✓ **Hyponatraemia**: < 135 mEq/l (operational value < 130 or a decreasing trend)
- ✓ **Germinal matrix haemorrhage and Intraventricular haemorrhage** will be determined according to Papile's classification of cranial ultrasound findings of echodensity in the

germinal matrix or ventricular extension ⁽²⁴⁾.

- ✓ **Cerebral parenchymal haemorrhage** will be determined according to the cranial ultrasound finding of an echogenic lesion that fans out from the ventricular wall into the brain substance, associated to a GMH/IVH
- ✓ **Necrotizing enterocolitis** is defined as stage 2 or higher as per modified Bell's criteria ⁽²⁵⁾.
- ✓ **Neonatal jaundice is defined as** elevated total serum/plasma bilirubin (TB) levels, which results in yellowish discolouration of the skin, and/or conjunctiva caused by bilirubin deposition

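### SAP 6.1.4.8 requires a site diagnosis of BPD on top of 28 days of oxygen, so it can drop babies who meet the protocol's definition

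*SAP*

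**What the plan says.** Protocol Appendix IV sets the general criterion for BPD, assessed at 36 weeks PMA or discharge home if earlier: "treatment with oxygen > 21% for at least 28 days plus the below reported additional criteria". The additional criteria are grades. The lowest is "Mild BPD = breathing room air at 36 weeks PMA or at discharge", the next is "Moderate BPD = need for < 30% oxygen at 36 weeks PMA or at discharge", and the severe grade takes 30% oxygen or more and/or positive pressure.

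SAP 6.1.4.8 cites the same workshop criteria. It then counts a baby, and goes on to grade it, only under this rule: oxygen above 21% "for at least 28 days? ='Yes' and 'Did the patient have a diagnosis of BPD?='Yes". The composite in the same section is death by 36 weeks PMA, or survival to then with a BPD diagnosis. SAP 6.3.12.1.7 does not impute BPD for babies not assessed at 36 weeks and leaves missing cases out of the test. It says nothing about a baby with Yes on oxygen and No on diagnosis.

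At the 36-week visit, protocol 7.1.9 asks the site for "BPD diagnosis (see definition in Appendix II". Protocol 10.8 also sends the reader to Appendix II for study definitions. The protocol's list of appendices gives Appendix II as the principal investigator's approval page and Appendix IV as the definitions.

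If a discharged or transferred baby cannot be recalled, 7.1.9 tells the investigator to "contact the physician of the continuing care site or the family pediatrician to collect the relevant information". Protocol 10.11 asks for the continuing-care discharge letter, in part "to determine if the baby is suffering from BPD".

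**The concern.** BPD and death/BPD at 36 weeks stand under the main objectives in both documents, and Table 14.2.7 (mortality and BPD) is marked for the Key First Results package. The protocol defines BPD by a duration of oxygen and then grades it. The SAP adds a local Yes/No judgement that must also be positive. A baby who had 28 days of oxygen but is in room air at 36 weeks has mild BPD under Appendix IV, yet this is the baby a clinician is least likely to call a BPD case. If the diagnosis item is answered No, the SAP most naturally scores that baby as BPD-free, because only missing or unassessed cases leave the denominator.

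The reported rates would then reflect local labelling as well as the protocol condition, and would not be the rates the protocol describes.

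**Working it through.** The plan gives no BPD rate, effect size or power (protocol 12.1 states that no formal power calculation was done), so there is no figure to reproduce. The core check is logical.

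**Step 1. Do the grades cover everyone?** An assessed survivor with 28 days of oxygen is in room air, on less than 30% oxygen, or on 30% or more and/or positive pressure. No state is left over. So under Appendix IV, a Yes on 28-day oxygen plus an assessment always gives at least mild BPD.

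**Step 2. Compare the rules.** There are 2 oxygen answers × 2 diagnosis answers × 3 respiratory states = 12 combinations. Within each row the result is the same for all three states.

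| Oxygen 28 days | Diagnosis item | Protocol | SAP | Combinations |
|---|---|---|---|---|
| Yes | Yes | BPD | BPD | 3, agree |
| Yes | No | BPD | not BPD | 3, disagree |
| No | Yes | not BPD | not BPD | 3, agree |
| No | No | not BPD | not BPD | 3, agree |

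The rules disagree in 3 of 12 combinations, always with the SAP undercounting. The SAP cannot overcount relative to the protocol. Its wording could also be read as excluding discordant babies from the analysis instead of scoring them as non-cases; that too departs from Appendix IV.

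**Step 3. How many babies?** This is not known from the documents. Assume a protocol-defined BPD rate of 30% to 70%, treat all 126 babies as assessed survivors (a simplification that overstates the count), and let 5% to 30% of cases be answered No:

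- low end: 126 × 0.30 × 0.05 = 1.9
- high end: 126 × 0.70 × 0.30 = 26.5

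That is about 2 to 26 babies. If every site applies the definition, the number is 0.

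**Step 4. Effect on the BPD comparison.** Let a share *m* of true cases be lost equally in both arms. The relative risk is p1(1−m) / [p2(1−m)] = p1/p2, which is unchanged. The risk difference becomes (p1−p2)(1−m). Take assumed rates of 60% and 40%, n = 63 per arm and two-sided alpha 0.05, with

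power ≈ Φ{[Δ − 1.96√(2p̄(1−p̄)/n)] / √([p1(1−p1)+p2(1−p2)]/n)}.

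| Loss | Observed rates | RR | Risk difference | Power |
|---|---|---|---|---|
| 0% | 0.60, 0.40 | 1.5 | 0.20 | 61% |
| 10% | 0.54, 0.36 | 1.5 | 0.18 | 53% |
| 20% | 0.48, 0.32 | 1.5 | 0.16 | 45% |

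This is an unstratified approximation; the SAP's test is stratified by gestational age group. If the loss differs by arm, the relative risk is biased. With equal true rates and losses of 10% and 20%, it is 0.90/0.80 = 1.125 instead of 1.

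**Step 5. Effect on death/BPD.** Deaths are not lost, so the composite relative risk is [d1 + b1(1−m)] / [d2 + b2(1−m)], where *d* is the death rate and *b* the rate of survival with BPD. As *m* grows it moves towards d1/d2, the relative risk of death. Two assumed cases with 20% loss in each arm:

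- Deaths 10% in both arms, BPD 60% and 40% of survivors: (0.10 + 0.54)/(0.10 + 0.36) = 0.64/0.46 = 1.39 becomes (0.10 + 0.432)/(0.10 + 0.288) = 0.532/0.388 = 1.37, slightly closer to 1.
- Deaths 15% and 5%, with 50% surviving with BPD in both arms: 0.65/0.55 = 1.18 becomes 0.55/0.45 = 1.22, further from 1.

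**The case against.** The strongest reply is that the protocol itself words the composite (outline and section 8) in terms of a BPD diagnosis, and 7.1.9 tells the investigator to make that diagnosis by the study definition. On that view the SAP takes a protocol diagnosis and confirms it with the oxygen criterion. The answers should agree, and a discordant pair means a site error. This limits how often the rule matters, but does not rescue it. Because the diagnosis is tied to the study definition, a No alongside 28 days of oxygen is a wrong answer, and the SAP lets the wrong answer decide.

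Second, data management (protocol section 11) includes consistency checks, and the SAP refers several points to blinded data review. Discordant pairs may be caught there. That stands as a possibility. However, the SAP gives no rule for resolving them, and in 6.1.4.8 it cites the Data Review report only in the low-flow cannula note.

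A reader might also infer three stronger points that the documents do not support:

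- **That the undercount pulls the relative risk towards 1.** Equal proportional loss leaves the BPD relative risk unchanged, and the composite moves towards the relative risk of death, which may lie on either side. The trial is double blind, and nothing in the documents suggests loss that differs by arm.
- **That the answer usually comes from outside the study team.** Protocol 7.1.9 asks first for a visit at the recruiting site and allows outside contact only if that is not feasible. No frequency is given, and for those babies the oxygen answer may rest on the same outside sources.
- **That the wrong appendix pointer causes misclassification.** There is only one BPD definition in the protocol, and the list of appendices leads to it. The pointer is an error to correct; any effect on the data is conjecture.

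Whether pooling mild BPD with the higher grades is a good choice is a separate question about the definition, and is not an error in the plan.

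**Conclusion.** The concern holds as a mismatch between the SAP derivation and the protocol definition of an endpoint under the main objectives. The mismatch is certain from the text and runs one way: the diagnosis condition can only remove protocol-defined cases. Its size cannot be established. It is zero if sites answer by Appendix IV; the 2 to 26 babies and the power figures rest wholly on assumed rates and discordance.

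Where discordant answers occur and are scored as BPD-free, BPD and death/BPD rates fall, the BPD risk difference shrinks and power drops. Bias in the BPD relative risk needs loss that differs by arm.

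This should be fixed, but a reader should not infer that it invalidates the trial. The study is exploratory, names no single primary endpoint and has no power claim to undermine, and the number of babies affected is unknown.

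**What to change.** In SAP 6.1.4.8:

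- For survivors with a 36-week PMA assessment (or one at discharge home, if earlier), set BPD to Yes when the 28-day oxygen item is Yes.
- Grade it from the recorded supplemental oxygen and ventilatory support answers, keeping the low-flow cannula note.
- Keep survivors without an assessment as missing, as in 6.3.12.1.7. The 28-day item alone should not make them cases.
- Use the investigator's diagnosis only as a consistency check, and list discordant babies for blinded review.
- State that the composite uses this derived BPD variable.

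Correct the Appendix II pointers in protocol 7.1.9 and 10.8 to Appendix IV. A further row in Table 14.2.7 for death or moderate/severe BPD is optional.

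The cost is SAP wording, one derivation and one listing. It should need no new data, provided the oxygen and support answers were recorded whatever the diagnosis answer was; the eCRF is not among the documents, so check this first. Reported BPD rates could be somewhat higher. If the database is already locked, the SAP's own route for the change is an addendum giving the reason.
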